7.2.3 Evaluating Adverse Events

An investigator who is a qualified physician will evaluate all adverse events with respect to the elements outlined in [Table 5](#). The investigator's assessment of causality is required for each adverse event. Refer to [Table 5](#) for instructions in evaluating adverse events.

Table 5 Evaluating Adverse Events

Maximum Intensity	Mild	awareness of sign or symptom, but easily tolerated (for pediatric trials, awareness of symptom, but easily tolerated)
	Moderate	discomfort enough to cause interference with usual activity (for pediatric trials, definitely acting like something is wrong)
	Severe	incapacitating with inability to work or do usual activity (for pediatric trials, extremely distressed or unable to do usual activities)
Seriousness	A serious adverse event (AE) is any adverse event occurring at any dose or during any use of Sponsor's product that:	
	† Results in death; or	
	† Is life threatening; or places the subject, in the view of the investigator, at immediate risk of death from the event as it occurred [Note: This does not include an adverse event that, had it occurred in a more severe form, might have caused death.]; or	
	† Results in a persistent or significant disability/incapacity (substantial disruption of one's ability to conduct normal life functions); or	
	† Results in or prolongs an existing inpatient hospitalization (hospitalization is defined as an inpatient admission, regardless of length of stay, even if the hospitalization is a precautionary measure for continued observation. (Note: Hospitalization for an elective procedure to treat a pre-existing condition that has not worsened is not a serious adverse event. A pre-existing condition is a clinical condition that is diagnosed prior to the use of a Merck product and is documented in the patient's medical history.); or	
	† Is a congenital anomaly/birth defect (in offspring of subject taking the product regardless of time to diagnosis); or	
	Is a cancer (although not serious per ICH definition, is reportable to the Sponsor within 24 hours to meet certain local requirements); or	
	Overdose, although not serious per ICH definition, whether accidental or intentional, with or without an accompanying adverse event/serious adverse event, is reportable to the Sponsor within 24 hours to meet certain local requirements.	
	Other important medical events that may not result in death, not be life threatening, or not require hospitalization may be considered a serious adverse event when, based upon appropriate medical judgment, the event may jeopardize the subject and may require medical or surgical intervention to prevent one of the outcomes listed previously (designated above by a †).	
Duration	Record the start and stop dates of the adverse event. If less than 1 day, indicate the appropriate length of time and units	
Action taken	Did the adverse event cause the Sponsor's product to be discontinued?	
Relationship to Sponsor's Product	Did the Sponsor's product cause the adverse event? The determination of the likelihood that the Sponsor's product caused the adverse event will be provided by an investigator who is a qualified physician. The investigator's signed/dated initials on the source document or worksheet that supports the causality noted on the AE form, ensures that a medically qualified assessment of causality was done. This initialed document must be retained for the required regulatory time frame. The criteria below are intended as reference guidelines to assist the investigator in assessing the likelihood of a relationship between the test drug and the adverse event based upon the available information The following components are to be used to assess the relationship between the Sponsor's product and the AE; the greater the correlation with the components and their respective elements (in number and/or intensity), the more likely the Sponsor's product caused the adverse event:	
	Exposure	Is there evidence that the subject was actually exposed to the Sponsor's product such as: reliable history, acceptable compliance assessment (pill count, diary, etc.), expected pharmacologic effect, or measurement of drug/metabolite in bodily specimen?
	Time Course	Did the AE follow in a reasonable temporal sequence from administration of the Sponsor's product? Is the time of onset of the AE compatible with a drug-induced effect (applies to trials with investigational medicinal product)?
	Likely Cause	Is the AE not reasonably explained by another etiology such as underlying disease, other drug(s)/vaccine(s), or other host or environmental factors

Relationship to Sponsor's Product (continued)	The following components are to be used to assess the relationship between the Sponsor's product and the AE: (continued)	
	Dechallenge	Was the Sponsor's product discontinued or dose/exposure/frequency reduced? If yes, did the AE resolve or improve? If yes, this is a positive dechallenge. If no, this is a negative dechallenge. (Note: This criterion is not applicable if: (1) the AE resulted in death or permanent disability; (2) the AE resolved/improved despite continuation of the Sponsor's product; (3) the trial is a single-dose drug trial); or (4) Sponsor's product(s) is/are only used one time.)
	Rechallenge	Was the subject re-exposed to the Sponsor's product in this trial? If yes, did the AE recur or worsen? If yes, this is a positive rechallenge. If no, this is a negative rechallenge. (Note: This criterion is not applicable if: (1) the initial AE resulted in death or permanent disability, or (2) the trial is a single-dose drug trial); or (3) Sponsor's product(s) is/are used only one time.) NOTE: IF A RECHALLENGE IS PLANNED FOR AN ADVERSE EVENT WHICH WAS SERIOUS AND WHICH MAY HAVE BEEN CAUSED BY THE SPONSOR'S PRODUCT, OR IF RE-EXPOSURE TO THE SPONSOR'S PRODUCT POSES ADDITIONAL POTENTIAL SIGNIFICANT RISK TO THE SUBJECT THEN THE RECHALLENGE MUST BE APPROVED IN ADVANCE BY THE SPONSOR CLINICAL DIRECTOR AND THE INSTITUTIONAL REVIEW BOARD/INDEPENDENT ETHICS COMMITTEE.
	Consistency with Trial Treatment Profile	Is the clinical/pathological presentation of the AE consistent with previous knowledge regarding the Sponsor's product or drug class pharmacology or toxicology?
The assessment of relationship will be reported on the case report forms /worksheets by an investigator who is a qualified physician according to his/her best clinical judgment, including consideration of the above elements.		
Record one of the following:		Use the following scale of criteria as guidance (not all criteria must be present to be indicative of a Sponsor's product relationship).
Yes, there is a reasonable possibility of Sponsor's product relationship.		There is evidence of exposure to the Sponsor's product. The temporal sequence of the AE onset relative to the administration of the Sponsor's product is reasonable. The AE is more likely explained by the Sponsor's product than by another cause.
No, there is not a reasonable possibility of Sponsor's product relationship		Subject did not receive the Sponsor's product OR temporal sequence of the AE onset relative to administration of the Sponsor's product is not reasonable OR the AE is more likely explained by another cause than the Sponsor's product. (Also entered for a subject with overdose without an associated AE.)

7.2.4 Sponsor Responsibility for Reporting Adverse Events

All Adverse Events will be reported to regulatory authorities, IRB/IECs and investigators in accordance with all applicable global laws and regulations, i.e., per ICH Topic E6 (R1) Guidelines for Good Clinical Practice.

7.3 TRIAL GOVERNANCE AND OVERSIGHT

7.3.1 Scientific Advisory Committee

This trial was developed in collaboration with a Scientific Advisory Committee (SAC). The SAC comprises both Sponsor and non-Sponsor scientific experts who provide input with respect to trial design, interpretation of trial results and subsequent peer-reviewed scientific publications.

8.0 STATISTICAL ANALYSIS PLAN

This section outlines the statistical analysis strategy and procedures for the study. Changes to analyses made after the protocol has been finalized, but prior to study finalization, will be documented in a supplemental SAP (sSAP) and referenced in the Clinical Study Report (CSR) for the study. Post hoc exploratory analyses will be clearly identified in the CSR.

8.1 Statistical Analysis Plan Summary

Key elements of the statistical analysis plan are summarized below; the comprehensive plan is provided in Sections 8.2 to 8.12.

Study Design Overview	A phase III, multi-center, open label, single-group trial to investigate the efficacy and safety of MK-8962 (corifollitropin alfa) in combination with human Chorionic Gonadotropin (hCG) for initiation or restoration of puberty as assessed by increased testicular volume in adolescent males 14 to <18 years old with hypogonadotropic hypogonadism
Treatment Assignment	Open-label treatment with MK-8962. During 12 weeks of Priming phase, all subjects receive 100 µg (for subjects with body weight ≤ 60 kg) or 150 µg (for subjects with body weight > 60 kg) MK-8962 once every two weeks, followed by 52 weeks of combined treatment with MK-8962 and hCG (titrated to maintain appropriate Total T and E2 levels) twice a week.
Analysis Populations	Efficacy: Full Analysis Set (FAS), Completers Safety: All Subjects as Treated (ASaT) Pharmacokinetics: All-Subjects-Pharmacokinetically-Evaluable (ASPE)
Primary Endpoint(s)	Change from baseline (Day 1) to Week 64 in log-transformed testicular volume (measured as the sum of volumes of left and right testes by ultrasound);
Key Secondary Endpoints	N/A
Statistical Methods for Key Efficacy/Immunogenicity/ Pharmacokinetic Analyses	The mean change from Day 1 (Baseline) in log-transformed testicular volume will be evaluated by using a mixed model with a fixed effect for baseline and time point and a random effect for subject. The geometric mean increase from Day 1 to Week 64 in testicular volume and its 95% CI will be obtained by exponentiation.

Statistical Methods for Key Safety Analyses	The percentage of subjects with anti-MK-8962 antibodies and its exact 95% CI will be calculated using the exact binomial method of Clopper Pearson.
Interim Analyses	No interim analyses are planned
Multiplicity	No multiplicity adjustment is planned as this is an estimation study
Sample Size and Power	This is an estimation study. Assuming a screen failure rate of approximately 50-60%, approximately 30-40 subjects will be screened to enroll approximately 15. Assuming a discontinuation rate of 30%, it is estimated that 10 subjects will complete. If the discontinuation rate exceeds 30%, enrollment will be re-opened to assure the target number of completers. The total number of enrolled subjects shall not exceed 35.

8.2 Responsibility for Analyses/In-House Blinding

The statistical analysis of the data obtained from this study will be the responsibility of the Clinical Biostatistics department of the SPONSOR.

This trial is being conducted as a single-group, open-label study, i.e., subjects, investigators, and SPONSOR personnel will be aware of subject treatment assignments after each subject is enrolled and treatment is assigned.

The Clinical Biostatistics department will generate the allocation schedule(s) for study treatment assignment. Randomization will be implemented in an interactive voice response system (IVRS).

8.3 Hypotheses/Estimation

Objectives of the study are stated in Section 3.0. This is an estimation study, no hypothesis will be tested.

8.4 Analysis Endpoints

Efficacy and safety endpoints that will be evaluated are listed below, followed by the descriptions of the derivations of selected endpoints.

8.4.1 Efficacy/Immunogenicity/Pharmacokinetics Endpoints

Primary Efficacy Endpoint

The primary efficacy endpoint for this trial is the Change from Baseline (Day 1) to Week 64 in log-transformed testicular volume (measured as the sum of volumes of left and right testes by ultrasound).

Secondary Efficacy Endpoint

- Change from baseline in serum inhibin B concentrations at Week 64;
- Growth velocity at Week 36 and Week 64;
- Tanner Stage of pubertal development at Weeks 12, 36 and 64.
- Characterization of MK-8962 pharmacokinetics (based on serum MK-8962 concentrations) through 64 weeks of treatment.

- Characterization of testicular sonographic pattern reflecting pubertal development through 64 weeks of treatment;
- Changes from baseline in endocrine parameters (LH, calculated free testosterone, Total T, E2, SHBG, and AMH at Weeks 12, 36 and 64;

8.4.2 Safety Endpoints

Initial description of safety measures is provided in Section 4.2.3.2.

The pre-specified safety endpoint is the presence of anti-MK-8962 antibodies.

Events of Clinical Interest

Liver function: an elevated AST or ALT lab value that is $\geq 3 \times$ the upper limit of normal (ULN) and an elevated total bilirubin lab value that is $\geq 2 \times$ ULN and, at the same time, an alkaline phosphatase lab value that $< 2 \times$ ULN, as determined by way of protocol-specified laboratory testing or unscheduled laboratory testing.

Hypersensitivity reaction: a potential sign or symptom of a hypersensitivity reaction after injection of MK-8962 such as new emergent skin rash, urticaria, hypotension, allergic asthma, chest tightness, broncho-spasm, dyspnea, or wheezing. Minor localized skin rash not suggesting hypersensitivity will not be considered an ECI.

Other safety endpoints include:

- Change from baseline for laboratory safety parameters and vital signs;
- Clinical review of adverse events;
- Predefined limits of changes (PDLCs) for laboratory values. Details about the safety ranges for each parameter (hematology/biochemistry) will be specified in the sSAP.

8.5 Analysis Populations

8.5.1 Efficacy Analysis Populations

The Full Analysis Set (FAS) population will serve as the primary population for the analysis of efficacy data in this study. The FAS population consists of all randomized subjects who:

- receive at least one dose of study treatment
- have baseline and at least one post-baseline measurement of testicular volume
- have LH levels ≤ 3 IU/L during anytime of the study
- have received at least 36 weeks¹ of treatment (12 weeks of priming with MK-8962 followed by 24 weeks of combined treatment with MK-8962 and hCG) and have no more than 4 weeks from the last dose of MK-8962 when the last measurement is made

¹ This time point is based on the observations regarding changes in testicular volume in a study of males with HH pre-treated with recFSH for 4 months followed by 24 months of pulsatile GnRH therapy (equivalent of combined treatment with FSH and LH/hCG) [17].

A supportive analysis using the Completers population will be performed for the primary efficacy endpoint only if there are at least 5 completers. The Completers population comprises subjects who remained on the study treatment regimen and completed through Week 64.

Another supportive analysis using the modified Intent-to-Treat population will be performed for the primary efficacy endpoint. The modified ITT population comprises all randomized subjects who have received at least 36 weeks of treatment (12 weeks of priming with MK-8962 followed by 24 weeks of combined treatment with MK-8962 and hCG), and have baseline and at least one post-baseline measurement of testicular volume at ≥ 36 weeks of treatment.

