3.2 Secondary Objective(s) & Hypothesis(es)

In adolescent males 14 to <18 years old with HH, to evaluate the following parameters over 64 weeks of treatment with MK-8962 (in combination with hCG for the last 52 weeks):

- 1) **Objective:** the change from baseline in inhibin B concentrations.
- 2) **Objective:** growth velocity (height).
- 3) **Objective:** the change from baseline in Tanner Stage of pubertal development.
- 4) **Objective:** the change from baseline in levels of endocrine parameters (i.e., luteinizing hormone [LH], calculated free testosterone [T], total testosterone [Total T], estradiol [E2], sex hormone-binding globulin [SHBG], and anti-Müllerian hormone [AMH]).
- 5) **Objective:** testicular sonographic pattern reflecting pubertal development.
- 6) **Objective:** the PK of MK-8962 (based on serum MK-8962 concentrations).

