4.2.2.1 Rationale for Single Arm Design

HH is a rare disease affecting between 1-10:100,000 of all (male and female) live births [6]. Due to the small number of subjects with this disease, recruitment of a sufficient number of subjects for both a treatment and comparator arm would be challenging, likely limiting the size of the MK-8962 group and hence experience. Based upon prior information on MK-8962, as well as information on the natural history of HH in adolescent males, trial objectives can be met in a single-arm, non-controlled study. Rationale supporting the use of a single arm study for the use of MK-8962 in adolescent boys with HH is provided below.

Rationale for not including a placebo arm

HH is associated with extremely low levels of the pituitary hormones (FSH and LH) required for pubertal development, leaving the subject in an infantile developmental state. The psychosocial impact of this condition is significant, leading to depression, anxiety, sexual dysfunction and a lower quality of life, all of which improve significantly with treatment

[13]. The possible negative psychosocial impact in untreated subjects raises ethical considerations that preclude the use of a placebo in this trial.

Since it is possible that some patients diagnosed with HH could have constitutional delay of puberty—and therefore spontaneously progress through puberty—the lack of a placebo group could impact conclusions regarding proportion of patients responding to active treatment (i.e., overestimating treatment response). However, given the small size of a placebo group that could be recruited into this study, robust comparisons to placebo would be limited. Moreover, since no placebo group is planned, the study's enrollment criteria have been carefully crafted to avoid the inclusion of subjects with a constitutional delay of puberty that are misdiagnosed with HH.

The diagnosis of HH will be confirmed using physical findings as well as strict endocrine parameters (Section 5.1.2). The strict enforcement of these enrollment criteria will minimize the possibility of a misdiagnosis and ensure that spontaneous progression to puberty is an uncommon event in this trial. LH levels will be monitored during the study to identify any subjects with spontaneous recovery of endogenous pituitary function.

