It is also recognized that spontaneous improvement in HH resulting in improvement in the primary outcomes parameters is a possibility. However, in a review of 308 patients with confirmed HH that specifically looked for evidence of spontaneous reversal of HH, only 39 males and 5 female patients had any physiologic evidence of spontaneous improvement of endocrine functions [14]. When stricter criteria for spontaneous progression based on recovery of serum testosterone, menstrual cyclicity, and/or fertility were applied, the numbers dropped to 29 men and 4 women (~10%), and the earliest age at which this recovery was evident in males was 19.1 years (mean age - 28.3 years) [14]. Additionally, spontaneous reversal of function has not been reported in any treatment naïve subject [14]. Given these findings, it would be unlikely that changes seen in these subjects over the course of the current study would be the result of spontaneous reversal of the disease. As noted, LH levels will be monitored during the study to identify any subjects with spontaneous recovery of endogenous pituitary function. Subjects with LH levels >3 IU/L during the trial will be excluded from the analysis.

Based on the possible negative impact of withholding treatment, the use of strict inclusion criteria, and the low possibility of spontaneous improvement of HH, the use of a placebo in this trial is not planned.

Rationale for not including a comparator arm

The pharmacodynamic profile of MK-8962 had been shown to be similar to that of FSH, and has been well-documented in trials with women undergoing COS [7], [8], [9] and in Trial P031 [10] of adult males with HH. In addition, the use of FSH preparations to induce testicular maturation and pubertal development in the adolescent HH male population is well-documented in the literature [1, 15, 16]. Therefore, it is anticipated that MK-8962 use should result in changes in testicular development that are similar to what is seen with recFSH.

Given the small population available to enter the trial, the robustness of any comparison to recFSH would be very limited. In addition, the strong evidence for appropriate FSH activity of MK-8962, and the prior literature studies looking at response to FSH in this population, support that the single arm study being implemented here should be interpretable.

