- Testicular echogenicity. Patients with HH or Kallmann syndrome have a hypoechogenic pattern of the testicular parenchyma, which becomes more normoechogenic with testicular maturation following gonadotropin treatment [22], suggesting that this endpoint may be useful to demonstrate maturation. The ultrasound pattern of the testicular parenchyma will be monitored for this change in this study to determine treatment effect. To date there is no generally accepted standard grading system for testicular echogenicity. To ensure standardization across the study sites, the ultrasound images will be read by a Sponsor-validated central imaging vendor. The assessments will be made according to a categorization system developed by the central imaging vendor and approved by the Sponsor, as described in the Independent Review Charter for imaging.
- Growth velocity (height measurement) and Tanner Stage of Development are well recognized markers for pubertal progress. These will be monitored in all subjects during this study. Details for the growth velocity and Tanner Stage assessment can be found in Section 7.1.2.

- Endocrine parameters to be measured in this study include calculated free T, Total T, E2, SHBG, and AMH. These hormones will serve as markers for the progress of puberty as a result from the study treatment.
- In addition, serum hCG levels will be measured to monitor treatment compliance. During the course of the trial, endogenous LH is expected to remain low in patients with HH. A subject with delayed puberty might experience pituitary maturation with MK-8962 and hCG treatment, which would result in an increase of the LH level. Therefore LH will also be measured during the trial to confirm the initial HH diagnosis.

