8.6.1 Statistical Methods for Efficacy Analyses

All efficacy analyses will be performed for the FAS.

This section describes the statistical methods that address the primary and secondary objectives. Methods related to exploratory objectives will be described in the supplemental SAP.

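### The secondary LH endpoint is summarized only in a population that excludes boys with LH above 3 IU/L, so the reported LH is capped and the number removed is not reported

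*Combined protocol and SAP*

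**What the plan says.** Section 8.4.1 lists among the secondary efficacy endpoints "Changes from baseline in endocrine parameters (LH, calculated free testosterone, Total T, E2, SHBG, and AMH at Weeks 12, 36 and 64"; Section 3.2 has the matching secondary objective. Section 8.6.1 fixes the population: "All efficacy analyses will be performed for the FAS". One condition for entering the FAS, in Section 8.5.1, is LH at or below 3 "IU/L during anytime of the study".

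Two places say why LH is measured. Section 4.2.2.1 states that "LH levels will be monitored during the study to identify any subjects with spontaneous recovery of endogenous pituitary function", and adds: "Subjects with LH levels >3 IU/L during the trial will be excluded from the analysis". Section 4.2.3.1 notes that a boy with delayed puberty might mature during treatment and show rising LH, and concludes: "Therefore LH will also be measured during the trial to confirm the initial HH diagnosis".

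Section 8.6.1.2 plans descriptive LH summaries by assessment and by treatment phase and names no population other than the FAS. The two sets without an LH condition, modified ITT and Completers, are specified in Section 8.5.1 for the primary endpoint only.

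**The concern.** LH is both an endpoint and a condition for being counted in that endpoint's analysis. A boy whose own axis starts to work during the trial, and whose LH passes 3 IU/L, leaves the table that would have shown it. A reader of the LH results would see uniformly low values and could not tell whether nobody crossed the threshold or whether those who did had been taken out.

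This matters more than usual because there is no control arm. Section 4.2.2.1 concedes that boys with constitutional delay could inflate the apparent response, and it offers strict entry criteria and LH monitoring as safeguards. How many boys crossed the protocol's own threshold is the direct evidence on how well those safeguards worked, and the plan does not report it.

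**Working it through.** **1. Meaning of the FAS condition.** Read literally, the phrase in Section 8.5.1 could mean LH at or below 3 IU/L at some time. Section 4.2.2.1 settles it: a value above 3 IU/L during the trial removes the boy.

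**2. What the LH table can show.** Entry requires LH of 2 IU/L or less (Section 5.1.2, criterion 7). For a boy with baseline LH of b IU/L, the largest rise that can appear in the FAS is 3 − b: at most 1 IU/L from a baseline of 2, and at most 3 IU/L from a baseline of 0.

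Illustration with assumed values: 15 boys with baseline LH 0.5 IU/L.
- Two rise to 5 IU/L and the rest do not change. The mean change in all treated boys is (2 × 4.5)/15 = 0.60 IU/L; in the FAS it is 0.00.
- One rises to 5 IU/L. The mean change is 4.5/15 = 0.30 IU/L against 0.00.

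**3. Whether another planned output fills the gap.**

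| Output | Covers post-baseline LH above 3 IU/L? |
|---|---|
| Modified ITT and Completers analyses (8.5.1) | No; testicular volume only |
| Safety laboratory summaries (Table 4, 8.4.2, 8.6.2) | No; LH is not in the safety panel, and the predefined limits concern hematology and biochemistry |
| Baseline characteristics (8.6.3.1) | No; LH as a baseline characteristic |
| Disposition (8.6.3.1, 8.6.3.2) | Not reliably; raised LH is not one of the listed reasons requiring discontinuation in 5.8 |
| List of exclusions with reasons (8.5.2) | Only for the pharmacokinetic population (ASPE); nothing equivalent for the FAS |

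**4. How often the rule might remove someone.** The nearest figure in the documents is the reversal rate in the review of 308 patients in Section 4.2.2.1: (29 + 4)/308 = 10.7%, which agrees with the stated approximate 10%. It is not a rate for this population. The same section reports an earliest male recovery age of 19.1 years and no reversal in treatment-naïve subjects. I therefore assume a range for p, the chance per boy of any LH above 3 IU/L.

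The number of boys also has a range. About 15 enrol, and with 30% discontinuation 15 × 0.70 = 10.5, which agrees with the plan's 10 completers. Boys treated for under 36 weeks leave the FAS in any case, so the number who could be removed because of LH alone lies between about 10 and 15.

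P(at least one removed) = 1 − (1 − p)^n:

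| p (assumed) | n = 10 | n = 15 |
|---|---|---|
| 1% | 1 − 0.99^10 = 10% | 1 − 0.99^15 = 14% |
| 5% | 1 − 0.95^10 = 40% | 1 − 0.95^15 = 54% |
| 10% | 1 − 0.90^10 = 65% | 1 − 0.90^15 = 79% |

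**5. What a count of zero would say.** With 0 of 15 boys above 3 IU/L, the exact two-sided 95% upper limit is 1 − 0.025^(1/15) = 22%. Even the most reassuring result needs its interval shown.

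**The case against.** The strongest reply is that detection and summary are different tasks. LH is read boy by boy; a value above 3 IU/L identifies the boy, and exclusion follows from that detection. A reader might infer that the trial cannot detect pituitary recovery at all. The documents do not support that: individual monitoring works as described, and rises up to 3 IU/L remain visible even in the FAS.

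A reader might also infer that the single-arm design depends on this LH table. It does not. Section 4.2.2.1 also rests on the ethics of withholding treatment, the small recruitable population, strict entry criteria and published experience, and nowhere says that the FAS mean LH will be used to show that recovery is rare.

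The exclusion is prespecified with a reason, and keeping boys with endogenous recovery out of a drug-effect summary is defensible. For that reason I would not extend the point to testosterone, inhibin B or Tanner stage. The primary endpoint has modified ITT and, with at least 5 completers, Completers analyses without the LH rule. Comparing the sizes of the FAS and modified ITT sets would hint at LH exclusions, but only roughly: the FAS also has a 4-week limit after the last MK-8962 dose, and modified ITT needs a measurement at 36 weeks or later.

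Moving LH to all treated boys also brings in those treated for under 36 weeks, so two selection rules change together. That is true; a list of FAS exclusions with reasons lets the reader separate them. Finally, a supplemental SAP could add the output. It could, but nothing in the current text plans it.

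Recovery being thought rare does not remove the gap. The reassuring figures concern reversal of confirmed HH, whereas Sections 4.2.2.1 and 4.2.3.1 also raise delayed puberty misdiagnosed as HH.

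**Conclusion.** The point holds as a defect in how one secondary endpoint is reported. Following the plan exactly gives an LH summary that cannot exceed the protocol's own threshold, with no statement of how many boys were removed to produce it. The cap follows from the population rule and does not depend on any assumed rate.

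How often it would matter does depend on assumptions. The chance that at least one boy is removed runs from 10% (1% per boy, 10 boys) to 79% (10% per boy, 15 boys), taking boys as independent with a common rate. The documents give no rate for this population and suggest the low end, so the upper figures should not be read as a forecast. Nothing here shows bias in the primary estimate or a need to change its population.

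**What to change.** In Sections 8.5.1 and 8.6.1:

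- Summarize LH in the All-Subjects-as-Treated (ASaT) population instead of the FAS.
- Report the number and percentage of boys with any LH above 3 IU/L during the trial, with an exact 95% CI (the Clopper-Pearson method already planned for antibodies).
- List those boys with the visit concerned and their change in testicular volume, together with every FAS exclusion and its reason, as Section 8.5.2 already requires for the ASPE set.

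Leave the FAS as it is for the primary endpoint and the other secondary endpoints. The cost is SAP wording, one table and one listing. The LH samples are already scheduled in the Trial Flow Chart, so no new data are needed. The change should be made before database lock.
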